- **B.2.0** Physical Activity is a Key Component of Managing Knee OA but Highly Underutilized. Many studies have confirmed that both aerobic and strengthening exercises improve pain, function, and other key outcomes among patients with knee OA ^{22,23}. A meta-analysis of clinical trials of exercise for knee OA found that pooled effect sizes (e.g., magnitude of treatment response) for aerobic exercise were 0.52 and 0.46 for pain and disability, respectively; for strengthening exercises, pooled effect sizes were 0.39 and 0.32, respectively ²⁴. These are medium-to-large effect sizes are comparable to those observed for pharmacological treatment of OA ²⁵. Based on this evidence, exercise is considered a cornerstone of managing knee OA ^{26,27}.

However, despite the strong evidence for exercise in managing OA symptoms, the majority of adults with OA are physically inactive ^{28,29}. In a recent study of adults who had or were at risk for knee OA, only 2% of African Americans and 13% of whites were currently meeting guidelines for physical activity ²⁹. Recent data from the Centers for Disease Control and Prevention (CDC) show that among US adults with arthritis (primarily OA), over half report doing 0 minutes of walking per week, and 66% reported <90 minutes of walking per week (which is the minimum amount of weekly walking shown in a randomized clinical trial to lower pain and improve function) ^{30,31}. In addition, health care providers often do not incorporate recommendations to exercise for patients with OA and other musculoskeletal conditions ^{32,33}. Primary reasons for low rates of exercise recommendations include: limited contact time with patients, lack of knowledge of clinical guidelines and appropriate exercises, and lack of support materials ^{34,35}. These barriers can all be addressed by the proposed internet-based exercise training program.

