C.8.1 General Overview. Our statistical approach is guided by the PCORI Methods Report. For the superiority hypotheses (H1, H3), analyses will be conducted on an intent-to-treat (ITT) basis; patients will be analyzed in the arm to which they were randomized, regardless of adherence, using all data up to the 12-month follow-up or last available measurement prior to exclusion or dropout ⁷⁹. Additional exploratory analyses focusing on alternative, more restrictive analytic cohorts (e.g., as treated) may be considered for the superiority hypotheses, to provide additional information about the impact of magnitude of exposure to the interventions. For non-inferiority hypotheses (H2, H4), the ITT analysis would not be the conservative approach; therefore, it is recommended to perform analysis on both an intent-to-treat and per-protocol basis ^{80,81}.

C.8.2 Descriptive statistics. Descriptive statistics, including graphical displays, will be used to summarize all

study variables overall and by randomization arm. We will construct individual and mean trajectory plots of the

longitudinal outcome variables to understand their general trends over the study period. In addition, we will explore the variability and correlation structure of the longitudinal outcome variables. All statistical analyses will be performed using the SAS (Cary, NC) software package / R (www.r-project.org).

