C.8.4. Specific Aim #1. H1 (Superiority): Patients who receive either IBET or standard PT will have clinically relevant improvements in pain, stiffness, and function, measured by the WOMAC at 4-month follow up, compared with patients in the WL control group; H2 (Non-Inferiority): The IBET intervention will be non-inferior to the standard PT intervention at 4-month follow-up, indicated by a mean WOMAC score less than 5 points higher than standard PT. For Specific Aim #1, we will use a linear mixed model (LMM) that accounts for the correlation between a participant's repeated measurements over time. Because of the small number of time points, we will apply an unstructured covariance matrix to take into account the within-patient correlation between repeated measures. The fixed-effect portion of the model will have the form: $Y_{it} = \beta_0 + \beta_1 4$ month+ β₂IBET*4month+ β₃PT*4month, where Y_{it} is the WOMAC score for subject i at t=0 and 4 months. We will estimate the parameters in the model and set up contrasts for tests of hypotheses using the SAS procedure MIXED (Cary, NC). Specifically, for H1, we will test for a difference in mean WOMAC scores between the IBET and/or PT group and the WL group at the primary time point of 4 months by testing that β_2 =0 and/or β_3 =0. For H2, we chose a non-inferiority limit of 5 points for mean WOMAC scores because it is reasonable and on the border of what would be considered a clinically important effect ⁸⁶. The null hypothesis in the non-inferiority framework is that IBET is inferior to standard PT in management of OA symptoms. We will test the noninferiority hypothesis by examining the estimate of the contrast β_2 - β_3 . Specifically, we will examine the 95% CI of the estimated contrast β_2 - β_3 , and if the upper limit of the interval is less than the threshold value of 5 points, we will conclude non-inferiority of IBET to PT 81. If we conclude non-inferiority, we test will for superiority of IBET to PT at 4 months by examining the 95% CI of the estimate of β_2 - β_3 for inclusion of 0 and the p-value for the test of the contrast β_2 - β_3 =0. Time is coded in this model to fit a constrained longitudinal data model (cLDA), in which baseline WOMAC score is modeled as a dependent variable in conjunction with the constraint of a common baseline mean across the treatment arms ⁸⁷. In this way, the cLDA model is comparable to an ANCOVA model; the two models are equivalent when there is no missing data. However, unlike an ANCOVA, participants who are missing follow-up measurements are included in the cLDA model because baseline is part of the response vector. For improvement in precision, the model will also be adjusted for enrollment site (stratification variable) 88. Similar procedures will be used to assess all continuous secondary outcomes. C.8.5. Specific Aim #2: H1 (Superiority): Patients who receive either IBET or standard PT will have clinically relevant improvements in pain, stiffness, and function, measured by the Western Ontario and McMasters Universities Osteoarthritis Index (WOMAC) at 12-month follow up, compared with patients in the WL control group; H2 (Non-Inferiority): The IBET intervention will be non-inferior to the standard PT intervention at 12month follow-up, indicated by a mean WOMAC score less than 5 points higher than standard PT. As

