
described above, will use a linear mixed model (LMM), adding in the 3 parameters for the 12-month period (12month, IBET*12month, PT*12month). We will follow the same testing procedures for the 12-month parameters as described for the 4-month. Similar procedures will be used to assess longer term effects of all continuous secondary outcomes at 12-months.

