
C.8.7. Additional Exploratory Analyses. We may also conduct exploratory analyses of associations among other measures collected as part of this study. This may include associations among variables at baseline, potential roles of baseline variables as moderators or mediators of treatment effects, or association of baseline variables with intervention uptake and outcomes.

C.8.8 Sample size. The sample size estimate of n=350 patients, 140 per each of the IBET and standard PT arms and 70 in the WL arm, is based on H2, the non-inferiority hypothesis, as this is the most conservative ^{80,94,95}, and on a randomization of 2:2:1 ⁹⁶. In our proposed analysis, this involves testing the IBET*4month and PT*4month interactions in our model. Sample size calculations are based on this comparison and use methods appropriate for ANCOVA analyses, which are equivalent in terms of efficiency to our linear model as noted above. in randomized trials 87. For the non-inferiority test the method is based on performing a one-sided twosample t-test sample size calculation at the alpha=0.025 level for the between group difference at the 4 month time point, multiplied by a factor 1-(rho)^2, where rho represents the Pearson correlation between baseline and follow-up time point outcome measures ⁹⁷. This sample size is then adjusted to compensate for potential missing observations due to attrition. Based on data from our other OA studies, we assume a correlation of 0.6 between WOMAC scores at baseline and at 4 months and an SD for WOMAC scores of 17.5. With 80% power, alpha=0.025, SD=17.5, rho=0.60, and a 10% attrition rate by 4 months, 140 patients in each of the IBET and standard PT groups, need to be enrolled at baseline to identify less than a 5 point difference in mean WOMAC scores between the two treatment groups. We selected the 10% attrition rate based our prior research of behavioral interventions for OA of similar duration ⁵⁴. For H1, with alpha=0.05, SD= 17.5, rho=.6, and approximately 10% attrition rate by 4 months, we have 80% power to detect moderate effect size of 0.35, corresponding to a 6.1 point difference (approximately 13% improvement, which corresponds to a clinically relevant difference) in mean total WOMAC scores at 4 months for either of the 2 intervention compared to WL

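### Does C.8.8 mislead by treating non-inferiority (H2) as the hypothesis that needs most patients, and is a rule needed for reading H2 with the wait-list contrasts?

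*Combined protocol and SAP*

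**What the plan says.** C.8.8 plans "n=350 patients, 140 per each of the IBET and standard PT arms and 70 in the WL arm" and states that this number "is based on H2, the non-inferiority hypothesis, as this is the most conservative". The inputs are SD 17.5, a baseline to 4-month correlation of 0.6, 10% attrition, 80% power and one-sided alpha 0.025. The same section then gives H1 80% power at alpha 0.05 for an effect size of 0.35, "corresponding to a 6.1 point difference (approximately 13% improvement, which corresponds to a clinically relevant difference", for each intervention against WL.

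C.8.4 sets the non-inferiority margin at 5 WOMAC points "because it is reasonable and on the border of what would be considered a clinically important effect". Its decision rule is: "if the upper limit of the interval is less than the threshold value of 5 points, we will conclude non-inferiority of IBET to PT". The same section tests each active arm against WL (β2 and β3, joined by and/or) in the same mixed model. For 12 months, C.8.5 says: "We will follow the same testing procedures for the 12-month parameters as described for the 4-month". C.8.1 analyses the superiority hypotheses by intention to treat. For the non-inferiority hypotheses it says "it is recommended to perform analysis on both an intent-to-treat and per-protocol basis".

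**The concern.** Under 2:2:1 allocation, a comparison of an active arm with WL is less precise than a comparison of the two active arms. The H1 effect (6.1 points) is not much larger than the H2 margin (5 points). It is therefore natural to doubt that H2 is the more demanding hypothesis. If H1 were harder, a trial sized on H2 could lack power for the question of whether either intervention works at all.

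The second part is about interpretation. Meeting the margin shows only that IBET is not more than 5 points worse than standard PT. If neither arm did anything, H2 would still be met in about 81% of trials. C.8.4 and C.8.5 do not say in words how H2 is to be read when a WL contrast fails. A reader who believes that H1 had power to spare might take the failed contrast as evidence of no effect.

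**Working it through.** **Inputs (C.8.8).** SD 17.5, correlation 0.6, attrition 10%, 2:2:1 allocation, 80% power. H2 is one-sided 0.025 with margin 5 (C.8.4). H1 is taken as two-sided 0.05 per arm; this reading reproduces the stated 80%, whereas a one-sided 0.05 test would give about 88%. The plan gives no true IBET minus PT difference for H2. Zero is assumed because it reproduces the plan's number.

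**Common terms.** Residual SD = 17.5 × √(1 − 0.36) = 14.0, so the variance is 196. (1.96 + 0.8416)² = 7.849.

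**The plan's H2 figure.** Evaluable n per active arm = 2 × 196 × 7.849 / 25 = 123.07, rounded up to 124. Then 124 / 0.9 = 137.8, or 138 enrolled per arm. The stated 140 is slightly above this.

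**The plan's H1 power.** With 10% attrition the evaluable numbers are 126/126/63.
- SE(arm − WL) = 14 × √(1/126 + 1/63) = 2.160.
- Power at 6.1 points = Φ(6.1/2.160 − 1.96) = 0.806, against the stated 80%.

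**Totals before rounding, 2:2:1, 10% attrition.**
- H2: 123.07 × 2.5 / 0.9 = 341.9.
- H1, with n in the active arm and n/2 in WL: n = 3 × 196 × 7.849 / d².
  - d = 0.35 × 17.5 = 6.125: n = 123.0, total 341.7.
  - d = 6.1 (the rounded figure): n = 124.0, total 345.
- The totals are equal when d = 5 × √1.5 = 6.124, almost exactly 0.35 SD.
- Rounded up to whole patients: H2 345; H1 345 at 6.125 and 350 at 6.1.

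**Power at 126/126/63.**
- H2: SE(IBET − PT) = 14 × √(2/126) = 1.764; Φ(5/1.764 − 1.96) = 0.809.
- H1 per arm at 6.125: Φ(6.125/2.160 − 1.96) = 0.809.
- At least one arm beats WL at 6.125: the two WL contrasts have correlation (1/63)/(1/126 + 1/63) = 2/3, and simulation puts both succeeding at 0.721. So 0.81 + 0.81 − 0.72 = 0.90.

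**Sensitivity to the zero-difference assumption.** If IBET is truly 1 point worse than PT, H2 needs 2 × 196 × 7.849 / 16 = 192.3 per arm, total 534. If IBET is 1 point better, it needs 2 × 196 × 7.849 / 36 = 85.5 per arm, total 237. The ranking of H2 against H1 therefore turns on a small assumption in either direction.

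**Reading H2 with H1.** H1 and H2 belong to the same aim. They are contrasts of the same fitted coefficients: β2 and β3 against WL, and β2 − β3 between the active arms. They are estimated at the same time points, and C.8.5 repeats the procedure at 12 months. An analyst following the plan obtains all three results together.

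**The case for a change.** The best case for a change is this. Per contrast, H2 is at most level with H1, so C.8.8 claims something that its inputs do not establish. At 5 points, which C.8.4 treats as borderline for clinical importance, H1 has power Φ(5/2.160 − 1.96) = 0.64 per arm and would need about 513 patients. Even the chance that at least one arm beats WL is 0.76 there, below the 0.81 for H2. If both arms are truly 5 points better than WL, H2 is met without PT shown better than WL in about 33% of trials (about 18% at 6.125 points). H2 and both WL contrasts succeed together with probability about 0.60 at 6.1 points and 0.44 at 5, and the plan states neither figure.

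These numbers are correct, but they do not show a fault. Five points is the margin for IBET against PT; C.8.8 names a separate H1 target, and any trial loses power below its planned effect. Nothing in the plan requires H2 and both WL contrasts to succeed together, so the joint figures answer a question that it does not pose. The pooled exercise effects in B.2.0 ("for strengthening exercises, pooled effect sizes were 0.39 and 0.32, respectively") are for pain and disability, not total WOMAC, so they cannot supply an H1 target in points.

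The point about reading H2 alone is sound in principle, and it is why a WL arm is useful. But that arm is in the design and H1 tests it by intention to treat. The H2 rule claims only non-inferiority to PT, not effectiveness. A sentence saying that effectiveness is claimed only for an arm that beats WL would restate H1.

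What stands is a matter of wording: the ranking of hypotheses in C.8.8 is not demonstrated per contrast.

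**Conclusion.** The concern does not call for a change. At the plan's stated H1 effect, H2 and per-arm H1 need the same total to within a fraction of a patient (341.9 and 341.7), and 350 covers both. The description of H2 as the more demanding is unproven per contrast. It is right if one arm beating WL is enough for H1 (power about 0.90 against 0.81). C.8.8 gives H1's power, effect and inputs openly, so a reader can see that H1 has 80% power per arm and no reserve; the smallest difference with 80% power is 2.8016 × 2.160 = 6.05 points.

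The missing sentence on joint reading is a gap that analysts fill sensibly, because the WL contrasts come from the same model at the same times. Rewording either place would alter no test, margin, alpha, power or sample size. A non-significant WL contrast should still be read from its confidence interval, as with any test.

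This rests on the plan's 4-month inputs, a normal approximation, a true IBET minus PT difference of zero for H2, and two-sided 0.05 per arm for H1.

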The PROMIS Sleep-related Impairment Instrument. The PROMIS adult sleep related impairment item bank focuses on self-reported perceptions of alertness, sleepiness, and tiredness during usual waking hours, and the perceived functional impairments during wakefulness associated with sleep problems or impaired alertness. It assesses sleep-related impairment over the past seven days. This scale includes 8 items, each measured on a 5-point Likert scale.

The PROMIS Fatigue Instrument. The PROMIS Fatigue instruments evaluate a range of self-reported symptoms, from mild subjective feelings of tiredness to an overwhelming, debilitating, and sustained sense of exhaustion that likely decreases one's ability to execute daily activities and function normally in family or social roles. Fatigue is divided into the experience of fatigue (frequency, duration, and intensity) and the impact of fatigue on physical, mental, and social activities. It assesses fatigue over the past seven days, This scale includes 8 items, each measured on a 5-point Likert scale.

Patient Global Assessment of Change. We will use the Patient Global Impression of Change scale to evaluate participants' perspectives on overall changes in their joint pain during the study period. This single-item measure asks participants to describe their change in pain on a 7-point rating scale with the following options: "very much improved," "much improved," "minimally improved," "no change," "minimally worse," "much worse," and "very much worse." This scale has been widely used in clinical trials of chronic pain treatments and is specifically recommended by IMMPACT ⁶⁶.

The Brief Fear of Movement Scale. The Brief Fear of Movement Scale is a six item scale for assessing fear of movement in OA. The scale specifically assesses activity avoidance due to pain-related fear of movement. All items are measured on a 4-point scale from "strongly agree" to "strongly disagree." Physical Activity Measures

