Physical Activity Scale for the Elderly. The Physical Activity Scale for the Elderly (PASE) is a self-report, 12-item scale that measures level occupational, household, and leisure activity during a one-week period. ⁷³ This scale was particularly developed for use among older adults; although all participants in the proposed study will not be age 65 or over, patients with knee OA typically have more limited physical activity than the general population. Therefore we believe this scale will be more applicable to our participant group than scales that were developed for younger adults.

Additional Self-Report Physical Activity Items. In addition to the assessment of overall physical activity that will be provided by the PASE, we are particularly interested in purposeful exercise behaviors that correspond to the IBET intervention and those typically prescribed in the context of standard PT for knee OA. We will ask participants, at each assessment point, to report the number of times and minutes per week, on average, they are completing strengthening, stretching, and aerobic exercises

Use of IBET Website / Number of PT Visits Attended. As described above, participants' use of the IBET website will be logged within the site. Therefore we will be able to compare use (e.g., number of log-ins and records of completion of exercise weekly) throughout the 12-month time period for participants in that study arm. Similarly, for patients in the Standard PT group, we will document the number of visits and the proportion of scheduled visits attended.

C.7.3 Process Measures. We will include two key process measures that have been associated with change in physical activity behavior. These will help us to understand potential mechanisms underlying any observed improvement in the IBET and / or standard PT interventions.

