control. For the remaining secondary outcomes we will also be powered to detect a moderate 0.35 effect size difference for either of the two intervention compared to the WL control group. We did not conduct a power analysis for the HTE analysis for Aim #3 because we are proposing a descriptive HTE ⁸⁹ and have followed the PCORI Methods Report on this issue. However, our analyses for Aim #3 will provide meaningful and practical data to Stakeholders and organizations with potential to incorporate the IBET program – for example, whether patients with different characteristics differentially benefit from IBET vs. standard PT for knee OA.

C.9.0 Data Management and Quality Control. Study tracking data will be entered into a database created by expert programmers at the UNC Sheps Center for Health Services Research, which has been developed and refined over many years in the context of other clinical trials. This database includes safeguards for ensuring tracking data are collected reliably for all participants (e.g., required fields, limited sets of appropriate responses) and will be thoroughly tested by the study team prior to beginning the clinical trial. This database can be easily customized for the proposed project. We are also able to randomize participants within this database. Customized reports allow the research assistant and project coordinator to identify daily tasks in need of completion, as well as generate flow charts to monitor overall study progress. Screening and outcome measures will be recorded in this same database. As with the tracking database, screening and outcome measures will be programmed to ensure reliable data (e.g., required fields, set ranges of responses) and will be thoroughly tested by the study team before beginning the study. The study team will conduct regular checks and cleaning of screening and outcomes data, throughout the study period, to monitor data quality. The database will also house information on study PT visits, including the initial evaluation form and progress notes for all visits.

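### C.8.8 says the remaining secondary outcomes are also powered for 0.35 SD versus wait list; for the PGIC, which has no baseline value, unadjusted power at that effect is about 62%, not the implied 80%

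*Combined protocol and SAP*

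**What the plan says.** Section C.8.8 (Sample size) sets out the method and then makes two power statements against wait list.

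- Method: a two-sample calculation "multiplied by a factor 1-(rho)^2, where rho represents the Pearson correlation between baseline and follow-up time point outcome measures".
- Value of rho: "we assume a correlation of 0.6 between WOMAC scores at baseline and at 4 months". No other outcome is given a correlation.
- H1, for WOMAC: "we have 80% power to detect moderate effect size of 0.35, corresponding to a 6.1 point difference", with alpha 0.05, SD 17.5, rho 0.6 and about 10% attrition by 4 months.
- Secondary outcomes, in the next sentence: "For the remaining secondary outcomes we will also be powered to detect a moderate 0.35 effect size difference". The comparison is again each intervention with wait list. There is no exception, no separate rho and no restated power level.

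Section C.7.2 (Secondary Outcomes) includes the PGIC, which records "overall changes in their joint pain during the study period". On its form: "This single-item measure asks participants to describe their change in pain on a 7-point rating scale".

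Section C.7.0 has a general statement that secondary outcomes are measured at baseline, 4 months and 12 months. Section C.8.4 applies the constrained longitudinal model, in which baseline is part of the response vector, to continuous secondary outcomes. It adjusts for enrollment site. Neither C.8.4 nor C.8.5 names a model for the PGIC or a baseline measure to adjust it for.

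**The concern.** The 80% at 0.35 SD depends on the precision gained by adjusting for the outcome's own baseline. The secondary-outcome sentence extends the result to every remaining secondary outcome. The PGIC has no baseline by construction: before treatment there is no change during the study to rate, and the general schedule in C.7.0 cannot supply one. The variance factor as C.8.8 defines it is therefore not available for this item.

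The PGIC is not an incidental measure. C.7.0 names global impression of change among the four IMMPACT pain outcome domains used to choose the outcomes. A reader who takes C.8.8 at its word would expect a true effect of 0.35 SD to be missed about 20% of the time. If the realistic figure is nearer 38%, a null PGIC result could be given more weight than it deserves.

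**Working it through.** **Inputs from C.8.8.** 140 per intervention arm and 70 on wait list; 10% attrition, so 140 × 0.9 = 126 and 70 × 0.9 = 63 completers; alpha 0.05; rho 0.6 (WOMAC); SD 17.5; effect 0.35 SD or 6.1 points. The plan does not state whether H1 is one- or two-sided. Two-sided reproduces the stated power, and one-sided gives 88.3%.

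**Formulas** (normal approximation, outcome in SD units).

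- SE = √(1 − r²) × √(1/126 + 1/63) = √(1 − r²) × 0.1543, where r is the correlation between the outcome and its baseline covariate.
- Power = Φ(effect/SE − 1.960).
- Effect detectable at 80% power = (1.960 + 0.8416) × SE.

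**1. The plan's own figure.** With r = 0.6, √(1 − 0.36) = 0.8 and SE = 0.1234. Then 0.35/0.1234 = 2.835 and Φ(0.875) = 80.9%. A noncentral t calculation gives 80.5%. The stated 80% for H1 reproduces.

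**2. The PGIC as an unadjusted linear score.** With r = 0, SE = 0.1543. Then 0.35/0.1543 = 2.268 and Φ(0.308) = 62.1% (noncentral t 61.7%). The effect detectable at 80% power is 2.8016 × 0.1543 = 0.432 SD. With no attrition (140 versus 70), SE = 0.1464 and power is 66.7%.

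**3. The PGIC adjusted for some baseline covariate** (the correlations are assumptions; the documents give none).

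| Correlation with PGIC | Power at 0.35 SD | Detectable at 80% power |
|---|---|---|
| 0.2 | 64% | 0.42 SD |
| 0.3 | 66% | 0.41 SD |
| 0.4 | 70% | 0.40 SD |
| 0.45 | 72% | 0.39 SD |

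**4. Correlation needed for 80% at 0.35 SD.** √(1 − (0.35/0.4323)²) = 0.587, or about 0.59. The same threshold applies to the secondary outcomes that do have a baseline.

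**5. A different effect scale** (assumption: the PGIC behaves like a WOMAC change score and the effect is the 6.1 points of H1). The change-score SD, in units of the WOMAC SD, is √(2(1 − rho)). At rho 0.6 this is 0.894, so the effect is (6.1/17.5)/0.894 = 0.39 SD.

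- Unadjusted power is 71% at rho 0.6, 62% at rho 0.5 and 83% at rho 0.7.
- The absolute correlation between baseline and change is √((1 − rho)/2) = 0.447 at rho 0.6. Adjusting for baseline WOMAC then gives 80.6%, the H1 figure for 6.1 points, because change adjusted for baseline is ANCOVA. At rho 0.5 the adjusted figure is 74%.

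**The case against.** The strongest reply is that nothing in C.8.8 is miscalculated. Its methods are described as suited to ANCOVA, C.8.4 and C.8.5 plan models only for continuous secondary outcomes, and the 80% is not repeated for them. The sentence could therefore be read as covering only outcomes analysed in that way. That is a reasonable guess at the intent. But C.8.4 uses the word continuous and the power sentence in C.8.8 does not, so the limit has to be written in. It does stand that the 80% is implied rather than stated.

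A second reply is that the shortfall depends on effect scale and model. This also stands in part. On the change-score reading in step 5 of the working, with adjustment for baseline WOMAC, the PGIC would reach about 81%. But that reading replaces the plan's 0.35 SD with 0.39 SD, assumes that the PGIC tracks WOMAC change, and needs a covariate that the plan does not name. At 0.35 PGIC SD the same adjustment gives 72%. Enrollment site is adjusted for, but C.8.8 credits it with no gain in precision.

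A third reply is that a seven-category item may be analysed with an ordinal model. The plan names none and gives no category distribution. Under assumed distributions, power is about 61 to 68% when 0.35 SD is set on the observed score, and about 52 to 65% when it is a shift on a latent scale. These figures show only that an ordinal model does not by itself restore 80%.

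A reader might infer three stronger things that the documents do not support:

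- That all the secondary outcomes are underpowered. For those with a baseline value the sentence holds if their correlation is about 0.59 or more, and nothing in the plan shows that it is lower.
- That the sentence also fails for website use and PT attendance, since for these "we will document the number of visits and the proportion of scheduled visits attended" or log-ins within one arm. The power sentence covers only comparisons with wait list, so these measures fall outside it.
- That the PGIC could never reach 80%. The change-score reading above shows that it could, under assumptions that the plan does not make.

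**Conclusion.** The concern holds for one listed secondary outcome. C.8.8 asserts, without exception, a detectable effect of 0.35 SD whose implied 80% power comes from a baseline correlation of 0.6 given for WOMAC only, and the PGIC has no baseline. As an unadjusted linear score its power at 0.35 PGIC SD is about 62%, and the effect it detects with 80% power is about 0.43 SD. This result uses only the plan's arm sizes, attrition and alpha (taken as two-sided), plus the absence of a baseline value. The adjusted, change-score and ordinal figures rest on assumptions from outside the documents.

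This is an overextended statement about the design, not a fault in the main calculation. H1 power for WOMAC reproduces. So does the H2 sample size: 124 evaluable per arm, and 124/0.9 gives 138 against 140 planned. The enrolment target does not depend on the PGIC. That a null PGIC result would be over-read is a risk; the plan itself draws no conclusion from one.

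**What to change.** In C.8.8:

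1. Limit the 0.35 SD sentence to continuous secondary outcomes that have a baseline value. State that it refers to 80% power and assumes a baseline to follow-up correlation of about 0.6 (at least 0.59).
2. Give the PGIC its own sentence: as an unadjusted linear score it detects about 0.43 SD with 80% power, and power at 0.35 SD is about 62%. If a covariate-adjusted or ordinal model is preferred, name it and give its figure, with the assumed covariate correlation or category distribution stated beside it.

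It would also help, though it is not essential, to name the follow-up-only model for the PGIC in C.8.4.

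The cost is one or two sentences, with no new data and no change to sample size. The downside is that the stated power becomes less favourable for the PGIC and openly conditional on the correlation for the other secondary outcomes.
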